3.1 Discussion of Study Design

This is a randomised, multi-centre, double-blind, placebo-controlled, parallel-group interventional trial in subjects with NCFB suffering from chronic infections with *P. aeruginosa*.

The trial will be conducted in approximately 100 sites in up to 15 countries. A total of 420 subjects (210 in each treatment group) are planned to be enrolled into the trial. The enrolment is competitive among sites.

At Visit 2 (within 30 days after Visit 1), eligible subjects with *P. aeruginosa* cultured from an initial sputum sample will be randomised in a 1:1 ratio to receive either colistimethate sodium or placebo.

It is planned that subjects will be contacted by phone 7 days after Randomisation (Visit 2) to determine if there are any issues with IMP administration and/or any initial AEs and will, thereafter, attend 5 further visits at the sites at 1, 3, 6, 9, and 12 months after Randomisation (i.e. Visits 3, 4, 5, 6, and 7) and will have 1 follow-up phone call at 12.5 months. Additional clinic visits, where feasible, and weekly phone calls will be conducted following pulmonary exacerbations until resolution.

The maximum expected duration of participation in the trial for an individual subject, from Visit 1 (Screening) to the follow-up phone call is up to 13.5 months. Treatment duration will be 12 months.

The start of the trial is defined as first subject in, i.e. Visit 1 for the first subject. The end of the trial is defined as the last subject out, i.e. when the last subject has the follow-up phone call.

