A fully blinded reassessment of trial size and power was undertaken for Promis I based on blinded data as of 15th January 2020 in 342 randomised, ITT population subjects. This evaluation gave a blinded annualised exacerbation rate estimate of 1.024 per year and an over-dispersion estimate of 0.273. For the hypothesised [CCI] reduction in the exacerbation rate with colistimethate sodium, this translates to annual event rate estimates for placebo and colistimethate sodium of 1.2701 vs 0.8256. The current data in Promis I, therefore, suggested that $n=145$ subjects per arm (290 total, unadjusted for dropout) were required to deliver 90% power, as compared to $n=170$ subjects per arm (340 total, unadjusted for dropout) stated in the protocol. Furthermore, the smallest observed reduction in the exacerbation rate with colistimethate sodium that will yield [CCI] in Promis I was computed to be [CCI].

This recalculation of the sample size was further refined to allow for a reduced overall exposure in Promis I arising due to some subjects dropping out of the study before completing 1 year of follow-up. This leads to a requirement for $n=188$ subjects per arm (376 total, adjusted for dropout) to detect a [CCI] reduction in the event rate with 90% power as compared to $n=210$ subjects per arm (420 total, adjusted for dropout) stated in the protocol; and with $n=188$ subjects per arm, the smallest observed rate reduction to yield [CCI] was computed to be [CCI].

It was, therefore, clear from the blinded data accrued in Promis I subjects to January 2020 that the $n=210$ subjects per arm stated in the protocol was unnecessarily high. At worst, the actual number of subjects required in Promis I is $n=188$ per arm (376 total) and this is inclusive of adjustment for the actual dropout rate seen in the trial itself. Given that, at the time of this sample size reassessment, a total of $n=372$ subjects had been randomised into Promis I, it could very reasonably be argued that very few, if any, further subjects were actually required to be randomised into the study to provide the required power to test the hypothesis that inhaled colistimethate sodium significantly reduces the exacerbation rate relative to placebo. Recruitment was, therefore, concluded with 377 randomised subjects.

CONFIDENTIAL

Sponsor:	Zambon S.p.A.	Protocol Number:	Z7224L01
----------	---------------	------------------	----------

4 Statistical Methodology

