4.1.4 Statistical Significance

The analysis of the trial is on a comparative basis. For all efficacy parameters, comparisons will be made between colistimethate sodium and placebo. Two-sided p-values <0.05 will be considered statistically significant and 95% two-sided confidence intervals (CIs) will be presented where appropriate. No adjustment for multiplicity testing will be adopted. A hierarchical testing procedure will be applied to the secondary endpoints as detailed in Section 4.7.5.

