In order to investigate whether the use of inhaled colistimethate sodium reduces the frequency of pulmonary exacerbations compared to placebo in subjects with NCFB chronically infected with *P. aeruginosa*, the following hypothesis will be tested:

- Null hypothesis: there is no difference between inhaled colistimethate sodium and placebo as regards the effect on the pulmonary exacerbation rate

CONFIDENTIAL

Sponsor:	Zambon S.p.A.	Protocol Number:	Z7224L01
----------	---------------	------------------	----------

- Alternative hypothesis: inhaled colistimethate sodium reduces the pulmonary exacerbation rate in favour of inhaled colistimethate sodium compared to placebo.

The null hypothesis must be rejected for the efficacy of inhaled colistimethate sodium to be considered demonstrated.

The number and the percentage of subjects with NCFB pulmonary exacerbations, the number of NCFB pulmonary exacerbations and the total follow-up time in years, as defined in [Section 4.1.7](#), will be summarised by treatment group.

The number of NCFB pulmonary exacerbations during the treatment period will be analysed using a negative binomial model including treatment, pooled site, i.e. country, as detailed in [Section 4.9.1](#), and use of stable concomitant therapy with oral macrolides as fixed effects and log-time on treatment as an offset. If there is a significant p-value ($p < 0.05$) observed for the country covariate in this primary analysis then the number of NCFB pulmonary exacerbations during the treatment period will also be analysed using a negative binomial model for each country separately with use of stable concomitant therapy with oral macrolides as a fixed effect and log-time on treatment as an offset.

The adjusted mean annual NCFB pulmonary exacerbation rates in each treatment group and the adjusted rate ratio with their 95% CIs will be estimated by the model. OBSMARGINS option will be used for the estimates. The number of subjects considered in the model will be provided by treatment group. An adjusted rate ratio < 1 will indicate that colistimethate sodium decreases the rate of pulmonary exacerbations compared to placebo. A two-sided Wald chi-square test p-value of < 0.05 will be considered statistically significant. P-values of the effects based on Wald chi-square test will also be presented.

The log-time on treatment in years will be calculated using the following formula:

- $\text{Log-time on treatment} = \ln(\text{Follow-up time})$.

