4.9.1 Site Effects

Sites will be pooled into clusters to fit the model in order to avoid estimation issues for too many degrees of freedom and levels with too low numbers of subjects included, considering that the estimated number of sites participating in the trial is approximately 80, the enrolment is competitive, and the total number of randomised subjects is approximately 420.

Given the similarity in geographic characteristics and concomitant treatments used (other than oral macrolides: i.e. bronchodilators, corticosteroids, etc) sites will be pooled into their corresponding countries.

Any change from this strategy will be discussed at the blind review meeting and documented in the Blind Data Review and Analysis Sets Report. In any case, pooling of the sites will not be data-dependent. The choice will be made based on medical consideration about the sites involved in the study.

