The number of subjects considered in the model in each treatment group will be presented. The value of δ at which the conclusion changes from favourable to unfavourable (i.e. where the p-value increases to above 0.05; that is, where the imputed number of pulmonary exacerbations in the Colistimethate Sodium group has to increase by 100 δ % for statistical significance to be lost) will be presented, along with the smallest value of δ for which the p-value remains below 0.05.

For each of these 2 values of δ , the adjusted mean NCFB pulmonary exacerbation rates and 95% CIs in each treatment group, the adjusted rate ratio and 95% CI, and the p-value from the multiple imputation analysis using that value of δ will also be presented.

6.1.2. **CCI** Analyses with Additional Covariates and Interactions

In order to explore the statistical evidence for the degree of consistency of treatment effect at each level of a given prognostic factor, the negative binomial model used for the primary analysis will be repeated with the following additional effects included (one model per bullet point below):

- Country-by-treatment interaction;
- Number of NCFB pulmonary exacerbations requiring oral or intravenous antibiotics in the 12 months prior to study entry (# exacerbations) (1; 2; >2) and # exacerbations-by-treatment interaction;
- Previous usage of colistimethate sodium/colistin (Yes; No) and previous usage-by-treatment interaction;

This document is confidential.

- Age (as a continuous covariate) and age-by-treatment interaction;
- Age group (<65 years; >=65 years) and age group-by-treatment interaction;
- Gender (Female; Male) and gender-by-treatment interaction.

As was done for the primary analysis, the adjusted mean annual NCFB pulmonary exacerbation rates in each treatment group and the adjusted rate ratio with their 95% CIs will be estimated by the model. The number of subjects considered in the model will be provided by treatment group. P-values of the effects and interactions based on Wald chi-square test will also be presented.

6.1.3. [REDACTED] Analyses by Subgroup

The primary model was already fitted separately for each country, for each # exacerbations (1; 2; >2), and for each previous usage of colistimethate sodium/colistin (Yes; No) category, as planned in Sections 4.7.4, 4.7.4.5 and 4.7.4.6, respectively, of the Final SAP v2.0 dated 8th April 2021.

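### SAP 4.7.4 triggers by-country analyses of the primary endpoint from the country main effect, which tests background rates and not whether the treatment effect differs by country

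*SAP*

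**What the plan says.** SAP 4.7.4 models the exacerbation count with treatment, country and oral macrolide use as fixed effects and log time on treatment as offset. There is no product term, and the sample code in SAP 4.14 has the same three effects. If p<0.05 is "observed for the country covariate in this primary analysis then the number of NCFB pulmonary exacerbations during the treatment period will also be analysed", the plan continues, "using a negative binomial model for each country separately with use of stable concomitant therapy with oral macrolides as a fixed effect" and the same offset. Country stands in for site because, under SAP 4.9.1, "sites will be pooled into their corresponding countries"; no minimum country size is set. On numbers, SAP 3.1 states: "The trial will be conducted in approximately 100 sites in up to 15 countries". SAP 3.9 states: "Recruitment was, therefore, concluded with 377 randomised subjects".

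For efficacy comparisons in general, SAP 4.1.4 states: "Two-sided p-values <0.05 will be considered statistically significant". It adds: "No adjustment for multiplicity testing will be adopted". The hierarchy in SAP 4.7.5 covers the primary and secondary endpoints and does not reach country results. SAP 4.7.4.4 calls its extra-covariate model exploratory; the by-country step carries no such label, and SAP 5.3.2 lists a table for it.

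The SAP Addendum was written after unblinding (its section 2.2). It reports in 6.1.3: "The primary model was already fitted separately for each country". It names three countries with no calculable rate ratio, and in 6.1.2 it adds a country-by-treatment interaction.

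**The concern.** The decision to look at treatment by country is tied to a statistic that answers a different question. In an additive model, the country term is significant when countries have different exacerbation rates, for example through case mix or local antibiotic practice. Such differences are plausible in a multinational trial and need not go with any difference in the rate ratio. The rule can therefore fire without heterogeneity, and it can miss heterogeneity that leaves country mean rates alone.

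Two further defects follow. Taken literally, the by-country model contains macrolide use and the offset only, so it estimates no treatment effect. If treatment is meant to be included, the plan produces a set of small-sample tests judged at 0.05, with no label saying how they are to be read. The check that does address consistency, the interaction, was defined only once results were known. That matters because Addendum section 3 gives internal consistency as an objective for an application resting on a single pivotal study.

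**Working it through.** **Inputs.** From SAP 3.9: annual rates 1.2701 (placebo) and 0.8256 (active), so the rate ratio is 0.8256/1.2701 = 0.65; dispersion k = 0.273; 377 randomised. From SAP 3.1: up to 15 countries, 1:1 allocation. From Addendum 6.1.3: three countries not estimable, so at most 15 − 3 = 12 ratios if all 15 took part. The documents give neither country sizes nor between-country SDs; those below are assumptions.

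**The plan's own figure.** n per arm = (1.960 + 1.282)² × [1/1.2701 + 1/0.8256 + 2(0.273)] / (ln 0.65)² = 10.51 × 2.545 / 0.1855 = 144.1. Rounded up, this is the 145 in SAP 3.9, so the inputs are read correctly.

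**What the trigger tests.** Write the log rate as α + β·treatment + γ_c + macrolide term. The trigger tests whether all γ_c are equal. Consistency of effect requires a test that all δ_c = 0 when β is replaced by β + δ_c. If country c has placebo rate λ_c and rate ratio ρ_c, the additive model's γ_c roughly follows ln[λ_c(1 + ρ_c)/2]. It moves with ρ_c when the λ_c are equal, and not when λ_c(1 + ρ_c) is constant. That is the only route by which heterogeneity reaches the trigger.

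**Simulated behaviour.** Negative binomial counts with k = 0.273 and 373 or 377 subjects; 15 countries, either equal or unequal in size (2 to 80 in the runs with 373 subjects); 300 to 600 trials per scenario (simulation error about 2 to 3 points).

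| Assumed scenario | Trigger, equal sizes | Trigger, unequal sizes | Interaction test |
|---|---|---|---|
| Same ratio everywhere, SD of log rate 0.2 | 53–58% | 45–48% | 2.5–9% |
| Same ratio everywhere, SD 0.4 | 97–99% | 91–93% | 3–9% |
| Same ratio everywhere, SD 0.6 | 100% | 99% | 2.5–7% |

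Twelve equal countries gave 63%, 98% and 100% for the trigger and 3–5% for the interaction test. With no background differences at all, the trigger fired in 4–6%, as it should.

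With real heterogeneity (SD of log rate ratio 0.5):

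- Equal placebo rates: trigger 52–61%, interaction test 64–73%.
- Country means over both arms held equal: trigger 7–12%, interaction test 67–69%.

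**By-country tests with no drug effect.** For m independent tests the chance of at least one p<0.05 is 1 − 0.95^m: 46.0% for m = 12 and 53.7% for m = 15. Simulation gave 42–43% (12 equal countries), 48–51% (15 equal) and 34–38% (15 unequal). Where the trigger fires often, conditioning on it leaves these figures about the same.

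**Information per country.** With 12 equal countries, 377/24 = 15.7 per arm and SE(log ratio) = √(2.545/15.7) = 0.402. Power at a true ratio of 0.65 is then about 19%, and the chance that one country's estimate exceeds 1 is 14%. The chance that at least one does is 1 − 0.858^12 = 84%.

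**The case against.** Efficacy rests on one null hypothesis and one test. The by-country fits are supplementary, gate nothing, and leave the primary alpha alone. A reader might infer that the rule leads to country-level efficacy claims, but no text in the SAP ties a claim to a country p-value. SAP v2.0 also never says that the split is meant as a consistency check. Both points stand and limit the weight of the issue.

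A reader might infer that the trigger carries no information about heterogeneity. That is too strong: with equal placebo rates it fires in roughly 55–60% of heterogeneous trials, not far below the interaction test. The low figure of about 10% needs the special case in which country means do not move.

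A reader might also count 15 uncontrolled tests. Addendum 6.1.3 reduces that to at most about 12 if all 15 countries took part. Nor should apparent reversals in single countries be blamed on the trigger: they come from small numbers, and a forest plot would show the same ones.

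The omission of treatment from the by-country model is probably a drafting slip, since rate ratios by country were produced. It still leaves the plan's text not describing what was fitted.

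Finally, the Addendum supplies an interaction model, a forest plot by country, and a caveat that the trial lacks power for subgroups. This is most of the remedy, but it came after unblinding and does not correct the rule in SAP v2.0.

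**Conclusion.** The rule in SAP 4.7.4 is wrong as written: it uses a test of background rates to decide on by-country treatment analyses, and the model it then specifies omits treatment. Under one common rate ratio, the trigger fires in roughly 45–60% of trials at an assumed SD of log rate of 0.2 and in 91–99% at 0.4; an interaction test fires in about 3–9%. Under real heterogeneity (assumed SD of log rate ratio 0.5) it fires in roughly 55–60% or about 10%, depending on whether country means shift, against about 65–70% for the interaction test. With no drug effect, at least one country reaches p<0.05 in roughly 35–50% of trials. These sizes rest on assumed country sizes and SDs. The direction does not, because it follows from the model having no interaction term. The primary result and its error rate are untouched, and no formal efficacy claim depends on these fits.

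**What to change.** In SAP 4.7.4:

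- Delete the country main-effect trigger.
- Name a treatment-by-country interaction, added to the primary model, as the check of consistency. Group small countries by a rule fixed blind, which SAP 4.9.1 already allows for through the blind review meeting. Grouping is needed: Addendum 6.1 reports unusable confidence intervals for the adjusted means because some countries had very few subjects.
- Name treatment in the by-country model.
- Present country rate ratios with 95% CIs whatever any p-value shows, labelled exploratory and without significance claims.

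The cost is wording and one model term. The small downside is that by-country p-values are no longer shown. Because this trial is already unblinded, the interaction in the Addendum stays post hoc and should be reported as such, and the country results already produced should carry the exploratory label.

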Sample Size:	A total of 420 randomised patients (210 per group) is foreseen assuming a withdrawal rate of approximately 20%, to achieve a total number of completed patients of 170 per group. For the primary endpoint of frequency of exacerbation (FOE), and a Poisson regression allowing for over-dispersion for FOE, with a two-sided significance level of 0.05, a treatment effect of 35% and a follow-up time of 1 year, with an FOE of 1.09 in the placebo group, this sample size will provide a power of 90%.

If the treatment difference effect size is 30% between the colistimethate sodium and placebo groups, the power with 170 completed patients per group will be 80%.

Population:Inclusion Criteria:

Subjects are eligible if they:

1. are able and willing to give informed consent following a detailed explanation of participation in the protocol and signed consent obtained;
2. are aged 18 years or older of either gender;
3. are diagnosed with NCFB by computerised tomography (CT) or high resolution CT (HRCT) as recorded in the subject's notes and this is their predominant condition being treated;
4. had at least 2 NCFB pulmonary exacerbations requiring oral or inhaled antibiotics or 1 NCFB pulmonary exacerbation requiring intravenous antibiotics in the 12 months preceding the Screening Visit (Visit 1) and had no NCFB pulmonary exacerbation with or without treatment during the period between Visit 1 and Visit 2;
5. have a documented history of *P. aeruginosa* infection;
6. are clinically stable and have not required a change in pulmonary treatment for at least 30 days before the Screening Visit (Visit 1);
7. have pre-bronchodilator FEV₁ ≥25% of predicted;
8. had a positive sputum culture for *P. aeruginosa* from an adequate sample taken at the Screening Visit (Visit 1) or during the screening period.

Exclusion Criteria:

Subjects are not eligible if they have/are:

1. known bronchiectasis as a consequence of cystic fibrosis (CF);
 2. known history of hypogammaglobulinaemia requiring treatment with immunoglobulin, unless fully replaced and considered immunocompetent by the Investigator;
 3. myasthenia gravis or porphyria;
 4. severe cardiovascular disease such as severe uncontrolled hypertension, ischaemic heart disease or cardiac arrhythmia and any other conditions that would confound the evaluation of safety, in the opinion of the Investigator;

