4.7.6.4 CCI

A single endpoint of the number and the percentage of subjects with severe CCI will be presented. CCI documented on the CCI form of the eCRF are presumed to include episodes of pneumonia which require intravenous antibiotics and/or hospitalisation. CCI form of the eCRF that is linked to an adverse event with a Preferred Term of 'Pneumonia' but does not have any associated intravenous antibiotics or hospitalisation will be assumed to be a CCI. Data will be reviewed during the blind review meeting and documented in the Blind Data Review and Analysis Sets Report.

A CCI will be defined as treated with systemic antibiotic therapy if a treatment is recorded in the Systemic Antibiotic Therapy form of the eCRF.

The corresponding adjusted mean annual CCI rate estimated by a negative binomial model with the same characteristics as the primary efficacy model as detailed in Section 4.7.4 will be analysed. The adjusted mean annual CCI in each treatment group and the adjusted rate ratio with their 95% CIs will

CONFIDENTIAL

Sponsor:	Zambon S.p.A.	Protocol Number:	Z7224L01
----------	---------------	------------------	----------

be estimated by the model. An adjusted rate ratio <1 will indicate that colistimethate sodium decreases the rate of CCI compared to placebo. A two-sided Wald chi-square test p-value of <0.05 will be considered statistically significant. P-values of the effects based on Wald chi-square test will also be presented.

The above summary/analysis will be performed using the mITT Population.

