- EoT should be replaced by the last time (in days) to event >270 days (if any);

- **Tables that require Cox proportional hazards model and 95% CIs of hazard ratios between treatments:**

*PROC PHREG data=dset;
CLASS treatment psite med;
MODEL time*event(1) = treatment psite med / ties=exact;
HAZARDRATIO 'Col. Sodium vs Placebo' treatment / cl=both;
BY byvar; (optional)
WHERE wherever; (optional)
RUN;*

Notes:

- Psite represents the pooled site, i.e. country, as detailed in [Section 4.9.1](#);
- Med represents use of stable concomitant therapy with oral macrolides (e.g. azithromycin or erythromycin or clarithromycin) (Yes/No);
- Time represents the time to event or time to censoring;
- Event represents the censoring indicator (1 = censored);
- If the option ties=exact requires a considerable amount of computer resources, the Efron approximation will be used (*ties=efron*).
- Treatment order: 1= Colistimethate Sodium, 2= Placebo.

CONFIDENTIAL

Sponsor:	Zambon S.p.A.	Protocol Number:	Z7224L01
----------	---------------	------------------	----------

- **Tables that require negative binomial modelling, including 95% CIs of treatment ratios:**

```
PROC GENMOD data = dset;
  CLASS treatment psite med;
  MODEL count = treatment psite med / offset=log_years link=log dist=negbin wald
  type3;
  ESTIMATE 'Col. Sodium / Placebo' treatment 1 -1 / exp;
  lsmeans treatment / ilink cl diff exp om;
  BY byvar; (optional)
  WHERE wherever; (optional)
RUN;
```

Notes:

- Psite represents the pooled site, i.e. country, as detailed in [Section 4.9.1](#);
- Med represents use of stable concomitant therapy with oral macrolides (e.g. azithromycin or erythromycin or clarithromycin) (Yes/No);
- Count represents the total number of exacerbations for each patient;
- log_years represents the logarithm of the follow-up time in years;
- Treatment order: 1= Colistimethate Sodium, 2= Placebo.

- **Tables that require linear mixed model for repeated measures and 95% CIs of differences between treatments:**

```
PROC MIXED data = dset;
  CLASS treatment visit psite med sub;
  MODEL change = treatment visit treatment*visit psite med baseline/ s ddfm=kr;
  REPEATED visit / subject=sub type=un r;
  LSMEANS treatment treatment*visit / om at means cl slice=visit;
  LSMESTIMATE treatment
  'Col. Sodium / Placebo' 1 -1 / cl;
  LSMESTIMATE treatment*visit
  'Col. Sodium / Placebo: Visit 4' 1 0 0 0 -1 0 0 0,
  'Col. Sodium / Placebo: Visit 5' 0 1 0 0 0 -1 0 0,

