6.1. Primary Efficacy Endpoint and Analysis

The primary efficacy endpoint for this trial is the mean annual non-cystic fibrosis bronchiectasis (NCFB) pulmonary exacerbation rate, defined in detail in Section 4.7.1 of the Final SAP v2.0 dated 8th April 2021. The primary efficacy analysis was conducted using a negative binomial model including treatment, country and use of stable concomitant therapy with oral macrolides (Yes; No) as fixed effects and log-time on treatment as an offset. The planning of this analysis is described in Section 4.7.4 of the Final SAP v2.0 dated 8th April 2021.

This section describes the post-hoc CCI analyses intended to assess the degree of internal consistency of the overall trial primary efficacy endpoint analysis results across a range of baseline and prognostic factors.

The confidence intervals (CIs) of the adjusted mean pulmonary exacerbation rates according to the primary efficacy analysis were very wide (<0.001, >9999.999) in both the Colistimethate Sodium and Placebo groups. This is caused by the inclusion of country as an effect in the model, due to some countries having very few subjects, resulting in large standard errors. The negative binomial model used for the primary efficacy analysis will be repeated without the country covariate included, in order to obtain more robust CIs for the adjusted mean pulmonary exacerbation rates in each treatment group, and to demonstrate that those means are stable. The adjusted mean annual NCFB pulmonary exacerbation rates in each treatment group and the adjusted rate ratio with their 95% CIs will be estimated by the model. The number of subjects considered in the model will be provided by treatment group. P-values of the stable concomitant therapy with oral macrolides effect based on Wald chi-square test will also be presented.

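### Adjusted arm rates average log rates over countries: a country without events makes both arms' intervals unbounded, and otherwise the rates sit below the marginal annual rate; the rate ratio and primary test are unaffected

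*SAP*

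**What the plan says.** SAP 4.7.4 analyses the exacerbation count with a negative binomial model containing treatment, country and macrolide use, with log follow-up as offset and no interaction. For the adjusted arm rates and rate ratio, the "OBSMARGINS option will be used for the estimates". The code in SAP 4.14 carries this out as "lsmeans treatment / ilink cl diff exp om". Under SAP 4.9.1, "sites will be pooled into their corresponding countries"; any change goes to the blind review, and the choice of pooling is not to depend on the data. SAP 4.7.4 also plans an unadjusted arm rate: total events divided by total follow-up.

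Addendum 6.1, written after lock and unblinding, reports that the intervals of the adjusted arm rates "were very wide (<0.001, >9999.999) in both the Colistimethate Sodium and Placebo groups". It attributes this to countries with very few subjects and refits the model without country, labelled post hoc. A 2022 note to file then groups small countries and repeats the primary, missing-at-random, copy-reference and tipping-point analyses. SAP 4.7.6.4 takes the rate of severe events as "estimated by a negative binomial model with the same characteristics as the primary efficacy model". The imputation code in SAP 4.14 requests the same observed-margin LS means.

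**The concern.** The endpoint is a mean annual rate. The planned estimator for each arm exponentiates a weighted average of log rates, which is a different quantity and a fragile one. A country contributes to it in proportion to its size, but its coefficient is unbounded below when no events occur there. Both arms share that coefficient, so both fail together.

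At stake is the adjusted rate per arm and the absolute difference drawn from it. The diagnosis matters too. If small size alone were the cause, grouping would be the natural cure. If the averaging scale is the cause, grouping removes the symptom and leaves the arm rates too low.

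**Working it through.** **Inputs from the documents.** Rates 1.2701 and 0.8256 per year, pooled rate 1.024, dispersion 0.273, 377 randomised (SAP 3.9); dropout about 20% (Protocol summary). **Assumed, because the documents do not give them:** 15 countries of 70, 55, 50, 45, 40, 30, 25, 20, 14, 10, 7, 5, 3, 2 and 1 subjects (sum 377), and a between-country SD of the log rate of 0.2, 0.4 or 0.6.

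**1. The plan's own figure.** n per arm = (1.960 + 1.282)² × (1/1.2701 + 1/0.8256 + 2 × 0.273) / (ln 0.65)² = 144.1, rounded up to 145. SAP 3.9 states 145, so the rates and dispersion are used as given.

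**2. What produces the reported interval.** For a rate near 1, an upper limit above 9999.999 needs a log-scale SE of at least ln(10000)/1.96 = 4.7. A 3-subject country has weight 3/377 = 0.008, so its own coefficient would need an SE near 4.7/0.008 = 590. A small country with even one event has an SE of about 1. With no events the fit drives the coefficient towards minus infinity. At a base rate of 1.05 and a coefficient of −20, the SE is about 1/√(3 × 1.05 × e⁻²⁰) = 12,411, and the half-width of the LS mean's log interval is 1.96 × (3/377) × 12,411 ≈ 194.

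**3. How easily a country has no events.** Per subject-year, (1 + 0.273 × 1.024)^(−1/0.273) = 0.405. For countries of 1, 2 and 3 subjects the probability is 0.41, 0.16 and 0.07.

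**4. Simulation** (200 trials per setting). With the 3-subject country forced to zero events, both arms' intervals exceeded the reported bounds in 100% of trials. With at least one event in every country, including those of 1, 2 and 3 subjects, they did so in 0%. Without forcing, 61% to 68%.

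**5. Level of the estimate when every country has events.** Median ratio to the standardised rate from the full model (placebo arm; the LS-mean ratio is the same in the active arm):

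| SD | LS mean | LS mean, countries of 10 or fewer grouped | No country | SE of log rate ratio, full to no country |
|---|---|---|---|---|
| 0.2 | 0.957 | 0.966 | 0.998 | 0.1199 to 0.1234 (+3%) |
| 0.4 | 0.909 | 0.921 | 0.997 | 0.1213 to 0.1295 (+7%) |
| 0.6 | 0.836 | 0.851 | 0.998 | 0.1242 to 0.1393 (+12%) |

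A separate set of 300 trials per scenario, with assumed country sizes from 80 to 2, gave shortfalls of 3%, 9% and 15% at SD 0, 0.4 and 0.6. At SD 0 the shortfall comes from sampling error in the country coefficients.

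**6. Same fit, two summaries.** One simulated trial with a zero-event country of 3 subjects:

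- LS means 0.511 (active) and 0.654 (placebo), both intervals unbounded.
- Standardised rates 0.713 (0.582 to 0.874) and 0.912 (0.765 to 1.088); crude rates 0.698 and 0.921.
- Rate ratio 0.782 (0.598 to 1.022), finite; 0.713/0.912 = 0.782. The country term cancels in the ratio because the model has no interaction.

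**The case against.** The success criterion in SAP 4.7.4 is the Wald test of the rate ratio, and the arm-level means decide nothing. The plan already has a finite arithmetic arm rate, total events over total follow-up, tabulated for the mITT and PP populations. The no-country model does what the Addendum wants of it: its arm rates came within about 0.5% of the standardised ones. The Addendum labels its work post hoc, and the note to file keeps ungrouped countries in the tables it reruns for correction. Standardised rates would also be chosen after unblinding. An LS mean at average covariates is a legitimate quantity, and it is low only against the marginal annual rate.

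All of this stands, and it limits the point to the adjusted arm rates. It does not rescue them: the planned estimator gave no usable interval, and grouping keeps the log averaging.

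A reader might infer more than the documents support:

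- **That the primary result is in doubt.** It is not; the rate ratio and its test do not pass through the country average.
- **That a country is known to have had no events.** No document says so. It is inferred from the interval. Small size is an incomplete diagnosis rather than a wrong one, since tiny countries are where zero counts arise.
- **That the published point estimates are low by a known amount.** With a zero-event country the LS mean depends on where the solver stops. In one simulated data set with a standardised placebo rate of 1.649, it was 1.375, 1.280 or 1.121 at tolerances of 1e-4, 1e-8 and 1e-14, so 17% to 32% low on identical data.
- **That dropping country was a wrong repair.** It returns nearly correct arm rates. Its cost is a less precise rate ratio, which matters only if it replaced the primary model, and nothing says that it does.
- **That grouping was chosen to rescue the copy-reference result**, which had lost significance. The note gives the wide intervals as its reason.

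**Conclusion.** The point holds for the adjusted arm rates only and should be fixed. The log averaging follows directly from the specified code, and its failure in both arms is on record in Addendum 6.1. A zero-event country is the likely cause, on the strength of steps 2 and 4. Where every country has events, the shortfall against the marginal annual rate is about 3% to 16%. That range rests on assumed country sizes and an assumed SD of 0 to 0.6; the direction does not, because a geometric mean cannot exceed the arithmetic one.

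The severe-event model in 4.7.6.4 is more exposed because its events are rarer. At an assumed 0.2 events per year, 99% of simulated trials had at least one zero-event country, against 44% to 56% at 1.27 per year. The documents do not report what happened there, and neither the Addendum nor the note lists a rerun of that table.

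The 2022 grouping is a pooling choice made after unblinding, although SAP 4.9.1 says that pooling will not depend on the data. The note does not call it post hoc and gives no rule for which countries count as small.

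**What to change.** Keep the pre-specified model, rate ratio and Wald test. For each arm, report the standardised rate from that fit: set treatment to the arm for every mITT subject, predict the rate at one year as exp(Xb), and average, with a delta-method or bootstrap interval. The ratio of the two standardised rates equals the model's rate ratio exactly, so the tables stay consistent. Label this as a post-hoc change if it is introduced after unblinding.

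Do the same for the model in SAP 4.7.6.4. For the imputation tables, compute the log standardised rate and its SE in each imputed data set before combining.

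In the note to file, label the grouped-country analyses explicitly as post hoc and state the grouping rule. Keep the no-country model as a post-hoc sensitivity analysis, not as a replacement for the primary model. In the Addendum, report whether any country had no events.

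The cost is a few lines of code and some wording; the primary test does not change.
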